8.4.3.3 Multivariate Statistical Analysis Strategy

The following is a top level description of the (exploratory) analysis strategy; further refinements may be required once the number of endpoints and their distribution are known (i.e. data driven modifications to the planned analysis may be made during study reporting). Please consult the GSK study statistician for further details if required. Further details of the methodology used would be included in the CPSR.

- Whenever possible, to preserve the maximum amount of information contained within them, continuous variables should not be dichotomised.
- Imputed biomarker responses would be used in this analysis (e.g. responses below LLQ would be assigned $\frac{1}{2}$ LLQ).
- Missing data / covariate values: Given the exploratory nature and relatively small number of subjects strong simplifying assumptions will be made. A missing at random assumption will be made for response variables. Initially for simplicity, covariates that are missing would be replaced with the corresponding treatment arm mean. A possible extension may use multiple imputation methodology to sample 5 sets of complete cases (via MCMC sampling methodology since the missingness patterns are not expected to be monotonic), analyse each of the 5 datasets separately and combine them using Rubin’s rules (e.g. via SAS PROC MI and PROC MIANALYZE). This extension would be considered if the number of missing covariates is deemed large by the GSK study statistician.
- Two approaches would be attempted each aiming to explore the magnitude and duration of any GSK2245035 drug related as assessed using a range of endpoints. If the observed data do not permit their use or their assumptions are unlikely to be valid these methods may not be attempted.

- Profile regression (via the PReMiM R package) – see [Liverani \(2015\)](#).
 - Response variable: BAC LAR outcomes (continuous Primary endpoint(s)). Separate modelling for each of the two primary endpoints
 - For simplicity, the repeated measures aspect will be ignored and data from each visit for an individual will be assumed to be independent.
 - For display purposes the endpoints will be grouped by (biomarker) functional category listed in [Table 13](#); with the option to explore the inclusion of other variables via additional functional categories; for example but not limited to FeNo and diary card WM TNSS value(s).
 - If necessary biomarkers from a functional category may be omitted if there appears to be a larger amount of multicollinearity.
 - Log transformed data used, individual variables may be standardised prior to model fitting.
 - Treatment and visit information would not be provided to the model fitting process.
 - A desirable outcome is if the number of clusters roughly matches the treatment and visit combinations (approximately 6) and/or that individuals from the same treatment arms are consistently clustering together. Also it is desirable that the expected response associated with any “GSK2245035 clusters” is lower than “placebo clusters”.
- Unsupervised clustering of individuals and visits followed by Canonical Correspondence analysis / Principal co-ordinates analysis to identify patterns when grouping results by treatment and visit – See [Valles \(2014\)](#)
 - The strategy described in [Valles \(2014\)](#) would be modified to reflect the continuous data in this study (rather than binary presence/absence in their data).
 - Each variable may be standardised prior to model fitting.
 - For each subject and visit combination their associated two primary response variables and the potential set of biomarkers described above for profile regression (plus the option to include other variables, for example but not limited to FeNo and diary card WM TNSS value(s)) would be put through an unsupervised clustering algorithm and the resulting dendrogram would also identify the timepoint and treatment associated with each sample

as well as colour coding by the standardised absolute values (see Fig 3 of the [Valles](#) (2014) paper).

- Additionally Canonical Correspondence analysis / Principal coordinates analysis would be used to explore patterns in samples belonging to the same treatment and visit. As in Fig 4 of [Valles](#) (2014) convex hulls may be drawn around the data points relating to samples from each treatment and timepoint combination and the areas of overlap determined and compared. Separately for each treatment arm and taking its respective Screening visit convex hull area as a reference, the area of overlap from the follow up visits would be expressed as a percentage of screening. Additionally and separately for each visit the convex hull area of GSK2245035 would be expressed relative to the Placebo convex hull area. The relative changes in these areas can potentially inform on magnitude and duration of treatment effects.
- Desirable outcomes would be distinct clusters by treatment arm(s) and lasting changes (across FUV1, FUV2 and FUV3) in convex hull areas on active that are not observed on the placebo.

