8.4.2.1 Biomarkers supporting the BAC related exploratory objective(s)

8.4.2.1.1 Sputum

Analyses described in Section 8.4.2.1.1 will use the Sputum producers population. If this population is deemed too small (e.g. less than 3 evaluable subjects per treatment arm/strata combination) a review of each of the planned modelling activities may take place to determine which (if any) of them would be attempted.

Cell Pellet: Sputum Differential cell counts

These analysis models assume all of the required data manipulation steps have been completed and that two response variables are derived per subject; namely a (derived) Total count (in Cells/g sputum – sometimes referred to as Absolute counts in display titles) and a Percentage (% of the Total Non-Squamous Cells). It is expected that a large proportion of subjects may not produce samples and/or viable/evaluable samples at all of the planned timepoints. **Inspection of the amount and pattern of missing data will be conducted, to determine if any form of statistical modelling should take place.** Note: The data manipulation steps add on a small constant in the eventuality that zero counts were recorded for a cell type so there should be no value that cannot be subjected to a log transformation.

Descriptive summary tables will be produced for “%” and Absolute count versions of the endpoints.

Figures of type PD_F1 and PD_F2 should be produced for each combination of response variable (absolute and %) and the cell type (Eosinophils, Neutrophils, etc) using all of the available timepoints.

The most pertinent of the differential cell types are the Eosinophils; although the same modelling process would be attempted for the other cell types (Neutrophils, Lymphocytes, Macrophages, Bronchial Epithelial Cells and Total Non-Squamous cells).

Statistical analysis of “Pre-BAC” Samples

- Additional Figures of type PD_F3
- Separate Bayesian repeated measures mixed effect models (per response variable and cell differential type), with non-informative priors for all model parameters, will be fitted to each transformed response over the planned post Screening time points (FUV1, FUV2 and FUV3).
- Baseline: (Transformed) SV Pre-BAC
- The additional terms to include in the chosen “R” model (see Section 11.9.1) are:
 - Fixed Categorical: Intercept
 - Fixed Continuous Covariates: Baseline*Visit

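### SAP 8.4.3.3: filling missing clustering variables with the treatment-arm mean feeds the withheld arm label back in, so the exploratory cluster analyses can show partial grouping by arm with no drug effect

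*SAP*

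**What the plan says.** SAP 8.4.3.3 describes two exploratory approaches. In profile regression the response is a primary LAR endpoint and the biomarkers are the covariates. The second approach clusters the two LAR endpoints together with "the potential set of biomarkers described above for profile regression", then draws ordination plots.

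For missing values, responses are assumed missing at random, while "covariates that are missing would be replaced with the corresponding treatment arm mean". Multiple imputation is a possible later step: "This extension would be considered if the number of missing covariates is deemed large by the GSK study statistician".

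For the profile regression fit, "Treatment and visit information would not be provided to the model fitting process". The hoped-for results are that the number of clusters is close to the number of treatment-by-visit combinations, put at about six, and/or that "individuals from the same treatment arms are consistently clustering together". The second approach likewise hopes for clusters that are distinct by arm.

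On missing data, SAP 8.4.2.1.1 warns: "It is expected that a large proportion of subjects may not produce samples and/or viable/evaluable samples at all of the planned timepoints". Under Protocol 7.3.3, subjects who give no adequate sputum at screening need not try again. Under Protocol 7.3.2, nasal challenge is done at screening and follow-up visits 1 and 2 but not 3. SAP 11.13.11 and 11.13.12 assign the profile regression and clustering outputs to All Subjects, so sputum non-producers are included.

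**The concern.** Agreement between clusters and arms is informative only if the clustering variables do not already contain the arm. Keeping treatment out of the fit is meant to secure that. Arm-mean imputation undoes it: every imputed row in an arm receives the same values, and those differ from the other arm's values by chance even when the drug does nothing. Because sputum variables go missing together, one row can receive a whole block of such values.

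The section's purpose is to explore the size and duration of a drug effect across many endpoints. If grouping by arm can come from the imputation rule, a favourable picture would be hard to interpret where missingness is heavy.

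**Working it through.** **Inputs**
- 20 completers per arm: Protocol 4.3.
- Three follow-up challenges: Protocol 7.3.1.
- About six clusters: SAP 8.4.3.3.
- Missing fraction: not stated, so a range is assumed.
- Number of biomarkers: the final list is left open (SAP 8.4.2), so assumed.
- Within-subject correlation 0.5 and a nominal 5% level: assumed. The SAP sets no test for these analyses.

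**Step 1, the plan's own figure.** 2 arms × 3 follow-up visits = 6, which reproduces the stated cluster count (2 × 4 = 8 if screening is counted). Clusters are cut at k = 6 below.

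**Step 2, the mechanism.** Suppose half of the 20 subjects per arm have no sputum, so 10 are observed over three visits. With unit variance and within-subject correlation 0.5, the chance difference between the two arm means of one biomarker has SD √[2 × (0.5 + 0.5/3)/10] = √0.133 = 0.37. All 10 × 3 = 30 imputed rows in an arm share one side of that gap, on every sputum biomarker at once.

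**Step 3, null simulation A.** 20 per arm, three visits as rows, 26 biomarkers, 14 sputum ones missing as a block by subject-visit, no drug effect. Two read-outs are tested by permuting arm between subjects: association of six Ward clusters with arm, and distance-based separation of the arms. Ranges are across repeat runs.

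| Subject-visits missing sputum | 20% | 40% | 60% |
|---|---|---|---|
| Cluster–arm association, arm mean | 10% | 21–24% | 59% |
| Arm separation, arm mean | 20–24% | 68–69% | 97–99% |

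With a mean pooled over arms and visits, both stay near 3–7%.

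**Step 4, null simulation B, built differently.** 20 biomarkers (6 blood, 8 sputum, 4 lavage, 2 filter) plus two LAR endpoints, within-block correlation 0.3, 300 trials per row, 99 permutations each. The simulation standard error is √(0.05 × 0.95/300) = 1.3 points at 5% and √(0.25/300) = 2.9 points at 50%.

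| Missing data | Association, arm mean | Separation, arm mean |
|---|---|---|
| None | 3% | 2% |
| 10% at random | 6% | 12% |
| 20% at random | 15% | 35% |
| 30% at random | 25% | 62% |
| 50% at random | 68% | 98% |
| Sputum, 25% of subjects | 8% | 22% |
| Sputum, 50% of subjects | 27% | 61% |
| Nasal at FUV3 only | 7% | 16% |
| Nasal at FUV3 + sputum 25% | 11% | 33% |
| Nasal at FUV3 + sputum 50% | 35% | 82% |

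With the mean pooled over arms and visits, the same missing-data scenarios give 2–6% and 3–7%. The excess therefore comes from the imputation rule and not from the clustering or the permutation test.

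The grouping itself is partial. Mean cluster purity by arm is 0.62 with complete data. Under arm-mean imputation it is 0.67 (nasal at FUV3 + sputum 50%) and 0.70 (50% at random), against 0.60 and 0.59 with the pooled mean. The average adjusted Rand index stays at or below about 0.09.

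**Step 5, is a visit-specific mean pooled over arms enough?** In the step 3 set-up it holds arm separation at about 3–6%. But it produces false separation by visit in about 40–45%, 94–96% and 99–100% of trials, against about 6–8% with the mean over arms and visits. Visit is also withheld from the fit and also enters the hoped-for cluster count, so this only moves the leak.

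**The case against.** The strongest reply is that the section is openly exploratory and full of discretion. Arm-mean filling is offered as a first simplification; multiple imputation may follow if much is missing; either method may be abandoned if its assumptions look doubtful; collinear biomarkers may be dropped. SAP 8.4.2.1.1 calls for a look at sputum missingness before modelling, and SAP 11.6.2.3 allows other approaches when much is missing. The scenarios with the largest inflation are where these provisions would be expected to apply. This stands as mitigation but is not a safeguard. None of these provisions identifies the arm-mean rule as the problem, and the SAP does not say whether arm would be left out of the multiple-imputation model or how Rubin's rules would combine cluster solutions.

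It is also fair that the largest rates come from a distance test the SAP does not plan. Cluster–arm association is closer to the stated read-out and its rates are lower. Profile regression itself was not run. The rule speaks of covariates, so its use in the second approach, which has no response/covariate split, is an inference.

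A reader might further infer that arm-mean filling shrinks the convex hulls that the second approach compares. The evidence does not support that. In a null check the log active/placebo area ratio stayed centred near zero (−0.05 to +0.09, SD 0.4–0.7), average area did not fall as missingness rose (20.5, 21.6, 22.1), and any collapse onto one point would occur under pooled filling too.

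**Conclusion.** The point holds as a defect in an exploratory analysis. The stated rule puts the withheld arm label into variables whose grouping by arm is then inspected. False cluster–arm association rises from a nominal 5% to about 10%, 21–24% and 59% when the sputum block is missing in 20%, 40% and 60% of subject-visits; the more sensitive separation measure rises further. At 10% missing at random the effect is small (6% and 12%). These figures rest on assumed missingness, correlations and biomarker counts, on Ward clustering as a stand-in, and on tests that the SAP does not specify.

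Two stronger readings should be resisted. The documents do not support saying that any separation reported would be an artefact: the grouping produced is partial, the SAP sets no threshold or decision rule, and profile regression also looks for a lower expected response in clusters dominated by GSK2245035, where the LAR response is not filled by arm mean. Nor does the point reach the primary LAR inference or the 0.7 success criterion, and the univariate biomarker models in SAP 8.4.2 do not use this rule.

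**What to change.** In SAP 8.4.3.3:

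- Replace the arm mean with a mean pooled over both arms and all visits. A visit-specific mean is not suitable, for the reason in step 5.
- State that treatment and visit stay out of the imputation model if multiple imputation is used.
- Omit a variable at visits where it is not collected, such as nasal-challenge biomarkers at FUV3, instead of imputing it.
- Judge agreement between clusters and arms at subject level. The profile regression treats a subject's visits as independent, although they always share one arm.

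The cost is a few sentences in the SAP and no new data. The downside is that pooled imputation somewhat dilutes a true separation of the arms; that loss has not been quantified.

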### 4.2. Treatment Arms and Duration

- The study will consist of a screening period of up to approximately 4 weeks (involving two screening visits), a blinded treatment period of 8 weeks, followed by a follow-up period of up to 3 months. The total duration of the study for each subject will therefore be a maximum of approximately 6 months. All doses will be administered in the clinic.
- Approximately 24 subjects per treatment arm will be randomised in a 1:1 ratio to receive either i.n. 20ng GSK2245035 or placebo every week for the duration of 8 weeks.

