### 4.3. Type and Number of Subjects

- Subjects with allergic asthma who are sensitized to perennial or seasonal allergen(s) will be enrolled in the study. Based on the restriction of concomitant medications as shown in the exclusion criteria, the target population includes subjects with mild asthma not requiring maintenance treatment with inhaled corticosteroid who are able

to be treated with short acting beta2-agonist (SABA) alone for the duration of the study (up until the final follow-up visit).

- A sufficient number of subjects will be enrolled to ensure that 20 per treatment arm complete the 8 week study treatment period and the BAC at the one week follow-up visit (one week after the 8th dose of study treatment).

If subjects prematurely discontinue the study, additional replacement subjects may be recruited and assigned the next available randomisation number, at the discretion of the Sponsor, in consultation with the investigator.

Following the interim analysis, additional subjects may also be enrolled to counteract the impact of individuals not exhibiting an LAR response on placebo.

Accounting for replacements and interim analysis recommendations, the total number of subjects to be randomised in this study is not expected to exceed 60.

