
 • LAR: minimum <change from saline baseline> FEV₁ between 4-10 hours following allergen challenge at the three follow up visits (i.e. FUV1, FUV2 and FUV3). • LAR: weighted mean of <change from saline baseline> FEV₁ between 4-10 hours following allergen challenge at the three follow up visits (i.e. FUV1, FUV2 and FUV3). • Note: Text in <> added for clarity, since the wording in the protocol and objectives is familiar to clinical experts in the field, but may be confusing given there are also absolute FEV1 values measured at those times too. • Any transformation of a response variable is also expected to be applied to the corresponding baseline variable. Final decisions on transformations will be based on the observed data and model diagnostics • Any observations with missing model covariates (e.g. baseline) would be excluded from the model fitting process (i.e. also excluding the record from any centering of covariates) 	
Model Specification	

 • Each endpoint will be analysed separately using a Bayesian Mixed effects repeated measures model fitted within Proc MCMC in SAS using the following approach: • Assume equal variances across treatment arms and use a pooled estimate of residual 	

Exploratory Statistical Analyses: Repeated measures version LAR Primary analysis model

variability (i.e. a 3x3 Variance Covariance Matrix). Note: if the posterior predictive distributions produced to support the interim analysis suggest this assumption may be invalid then the modelling approach may be modified to estimate separate variance covariance matrices for each treatment arm.

- **Step 1:** Fit all three of the following models (report output from each model in the same listing – along with the DIC values and changes in DIC values between models). Using a combination of changes in the DIC criteria, **and expert judgment** (see Section 11.9.1), select a single model.
- R1: Intercept + Centre + Baseline*Visit + Treatment + Visit + Allergen Exposure + Treatment*Visit + Allergen Exposure*Visit + Treatment*Allergen Exposure + Treatment*Allergen Exposure*Visit
- R2: Intercept + Centre + Baseline*Visit + Treatment + Visit + Allergen Exposure + Treatment*Visit + Allergen Exposure*Visit
- R3: Intercept + Centre + Baseline*Visit + Treatment + Visit + Treatment*Visit
- See Section 11.4.2 for Baseline definitions (Screening visit 2 BAC endpoint).

Where in each of the models (R1, R2 and R3) the effects are:

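### Pooling each subject's visits as independent records raises the chance of arm-dominated clusters in the profile regression when there is no drug effect

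*SAP*

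**What the plan says.** SAP 8.4.3.3 describes two exploratory approaches meant to show the size and duration of any drug effect across many endpoints. In the first, profile regression, an LAR endpoint is the response and the biomarkers are covariates. As a simplification, "the repeated measures aspect will be ignored and data from each visit for an individual will be assumed to be independent". The fit is blind to arm: "Treatment and visit information would not be provided to the model fitting process".

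The SAP then says what would look favourable. "A desirable outcome is if the number of clusters roughly matches the treatment and visit combinations (approximately 6", and/or "individuals from the same treatment arms are consistently clustering together". In addition, "it is desirable that the expected response associated with any" active-drug cluster should lie below that of the placebo clusters. Missing covariates are to be filled with the mean of the subject's treatment arm. The second approach clusters the same kind of subject-visit records without supervision and again treats distinct clusters by arm as desirable. Neither approach has a chance benchmark.

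The design facts that matter are these:
- Parallel groups: "Approximately 24 subjects per treatment arm will be randomised in a 1:1 ratio" (Protocol 4.2), with recruitment set so that "20 per treatment arm complete the 8 week study treatment period" (Protocol 4.3).
- The LAR endpoints are measured "following allergen challenge at the three follow up visits (i.e. FUV1, FUV2 and FUV3" (SAP 8.1.2).
- Elsewhere the SAP treats these visits as correlated. The LAR repeated measures model in 8.1.2 has a 3x3 variance-covariance matrix, and the sputum models in 8.4.2.1.1 use unstructured matrices.
- SAP 8.4.3.1 also ignores repeated measures when drawing regression lines, but says that those lines are only a rough guide. No such caution is attached to the clusters.

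**The concern.** The analysis is meant to ask whether treatment separates subjects. What it clusters is subject-visit records, and up to three records of one subject share an arm by design. If a subject's visits are alike, the algorithm tends to put them together, so the effective unit in a cluster is the subject rather than the record. A cluster of 18 records may be only six people, and six people fall mostly into one arm by chance far more often than 18 independent records do.

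Withholding arm from the fit does not prevent this, because subject identity carries arm. A feature that the SAP would read in the drug's favour can therefore arise from correlation between visits alone. At stake is the interpretation of a planned output (Table 5.27, Figure 5.70 and Listing 100).

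**Working it through.** **The plan's own figure.** 2 arms x 3 follow-up visits = 6, which agrees with the SAP's expected number of clusters.

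**Inputs.** 20 completers per arm (Protocol 4.3), hence 40 subjects and 40 x 3 = 120 records. The documents give no within-subject correlation, so a range of 0 to 0.9 is assumed. Also assumed are 10 biomarkers plus one response, with between-variable correlation 0.3.

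**Exact check, with no clustering algorithm.** Take one cluster of 18 records.
- Independent records: P(14 or more from one arm) = 2 x (3060 + 816 + 153 + 18 + 1) / 2^18 = 8096 / 262144 = 3.1%.
- Six whole subjects: records come in threes, so 14 or more means at least 5 of 6 subjects. P = 2 x (6 + 1) / 2^6 = 14 / 64 = 21.9%.

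**Null simulation.** Each record is sqrt(rho) x subject effect + sqrt(1 - rho) x visit effect, with no treatment term. Variables are standardised and records are clustered without arm or visit. The SAP states no test, so a record-level chi-square of arm by cluster at a nominal 5% stands in for one: the sum of (O - E)^2 / E, with 6 - 1 = 5 degrees of freedom. Ward clustering cut at six, and k-means, stand in for the profile-regression partition.

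| Within-subject correlation | 0 | 0.3 | 0.5 | 0.7 | 0.9 |
|---|---|---|---|---|---|
| Record-level association, Ward (2000 runs) | 4.8% | 14.2% | 29.3% | 50.6% | 64.7% |
| Same, k-means (500 runs) | 4.6% | 14.6% | 27.8% | 38.4% | 58.8% |
| Any cluster of 12+ records at least 75% one arm (Ward) | 11.3% | 19.9% | 31.5% | 47.5% | 68.8% |
| Such a cluster dominated by the active arm | 5.9% | 11.3% | 18.2% | 30.3% | 47.9% |
| As above, and lower mean response than the other clusters | 2.9% | 5.7% | 9.0% | 15.4% | 24.8% |
| Subjects with all three visits in one cluster (Ward, 500 runs) | 4% | 14% | 30% | 63% | 98% |
| Association judged by permuting arms over whole subjects (Ward, 500 runs) | 4.4% | 5.2% | 6.4% | 5.0% | 6.4% |

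Two further simulations with Ward and six clusters gave 56% and 47% at correlation 0.7 for the record-level test. Cutting at four or eight clusters instead of six gave 38.3% and 60.4%.

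**A fit that chooses its own number of clusters.** A Gaussian mixture with 1 to 8 components chosen by BIC was run on the same null (100 trials per setting). With full covariance it returned one cluster every time and no association at any correlation from 0 to 0.85. With diagonal covariance it returned 2 to 4 clusters, and an association in 7%, 11%, 13%, 16% and 26% of trials at correlation 0, 0.3, 0.5, 0.7 and 0.85.

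**One visit per fit.** With 40 independent records and six clusters, the record-level test is positive in 3.4% of null trials. Even so, about 70% of those fits contain a cluster of four or more subjects that is at least 75% one arm.

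**The case against.** The strongest reply is that the SAP plans no test, threshold or claim here, so the tabulated rates belong to a test that nobody intends to run. The number of clusters is an output of a Dirichlet-process mixture, not a forced six. The favourable reading also asks for a lower response in the active clusters, and it speaks of individuals; three visits of one person are not several individuals. The section calls itself a top-level, exploratory description open to refinement, and says that the methods may not be attempted if their assumptions are unlikely to hold.

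Much of this stands. A reader might infer from the table that half of all trials of an inert drug would be called positive. The documents do not support that, because there is no declaration rule, the correlation is assumed and the partition is a stand-in. Letting the fit choose its clusters lowers the rate sharply, to nothing in one version. Requiring a lower response as well brings 30.3% down to 15.4% at correlation 0.7.

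Two things are left. The direction held in every setting that produced more than one cluster, including the diagonal mixture (7% rising to 26%). And the general safeguard names no check, while the independence assumption is adopted knowingly in the same section, although the SAP models correlated visits for the same endpoints elsewhere. Exploratory status excuses the lack of error control. It does not excuse a favourable criterion that correlation between visits can satisfy unaided.

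**Conclusion.** The rule is flawed, and this is more than missing detail: visits are pooled as independent, and same-arm clustering is then read as encouraging. Under no drug effect, within-subject correlation makes arm-dominated clusters more likely. On the stand-in six-cluster fit the record-level association is roughly 3, 6 and 10 times its nominal 5% at correlations of 0.3, 0.5 and 0.7. At correlation 0 there is no inflation. These sizes rest on the assumed correlation, the assumed biomarker structure, the substitute algorithm and the proxy test, and should be taken as indicative only.

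Three stronger readings are tempting and are not supported:
- That arm clusters will appear. Even at correlation 0.7, about half of null trials on the Ward fit show no association.
- That the scheme is tilted towards the drug. Chance clusters are as likely to be placebo clusters as active ones.
- That cluster-level LAR intervals will be too narrow. SAP 8.4.3.3 plans no such intervals, and none were calculated.

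The primary LAR conclusion is untouched. It comes from a separate model at the first follow-up visit, with one record per subject (SAP 7.1.2).

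A related weakness was not simulated. Filling missing covariates with the arm mean puts arm into inputs that are meant to be blind to it. The nasal challenge biomarkers are not scheduled at the third follow-up visit (SAP Table 11), so many records could be affected.

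**What to change.** Keep the pooled fit, which preserves the comparison across visits, and add a reference distribution to SAP 8.4.3.3:

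- Name one summary of arm clustering (for example the arm-by-cluster chi-square) and one of the response difference between active and placebo clusters.
- Recompute both with treatment codes permuted between whole subjects, keeping all visits of a subject together. Read the observed result as supportive only if it exceeds that distribution. In the simulations this brought the null rate back to 4.4% to 6.4% at every correlation tried.
- Make the missing-covariate imputation blind to arm, or repeat it within each permutation.
- Apply the same reference to the second clustering approach.

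Fitting one visit at a time is not enough alone. It loses the duration comparison and, as shown above, still leaves many arm-dominated clusters to the eye.

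The cost is SAP wording and modest computing. Because arm is withheld from the fit, the clusters need not be refitted for each permutation once the imputation is arm-blind. If arm-mean imputation is kept, each permutation needs its own imputation and fit.
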